5.2 Ruxolitinib dose modifications for toxicities

Ruxolitinib doses may be reduced in the event of toxicities. **The lowest permissive dose of ruxolitinib is 5 mg daily.**

Subjects with sclerotic GVHD have limited therapy options and may be willing to accept certain degree of toxicities. As such, this trial will allow treating physicians to use discretion regarding dose modifications of ruxolitinib but only under certain situations as specified in this section.

For subjects with grade 2 or lower hematologic or non-hematologic toxicities, ruxolitinib may be continued at the current dose or dose reduced by 50% at the discretion of the treating physician. Dose reduction by 50% (i.e. reduction to 5 mg BID in subjects receiving 10 mg BID) or temporary drug cessation is allowed in subjects with certain grade ≥ 3 hematologic or non-hematologic toxicities (see table below). Subjects who require drug cessation will resume ruxolitinib at a dose no higher than 5 mg BID for at least 2 weeks before resuming their previous dose. Subjects with grade 3-4 toxicities are required to undergo close monitoring with repeat testing of any abnormal laboratory or clinical parameter(s) within 2-7 days depending on specific circumstances.

Ruxolitinib dose modifications for toxicities

Toxicity (CTCAE Version 4.03) possibly, probably or definitely related to ruxolitinib	Dose modification	Subsequent starting dose
	Hematologic toxicities	
Grade 4 hematologic toxicities: (platelet count <25,000/ μ L, neutrophil count <500/ μ L, grade 4 febrile neutropenia with life-threatening consequences or requiring urgent interventions, life threatening anemia)	Temporary drug cessation until resolution to grade ≤ 2 or baseline ^a (mandatory)	5 mg BID for at least 2 weeks before considering dose escalation ^b
Grade 3 hematologic toxicities: (platelet count <50,000-25,000/ μ L, neutrophil count <1000-500/ μ L with or without fever [single episode of $>38.3^{\circ}\text{C}$ or $\geq 38^{\circ}\text{C}$ for more than 1 hour] without serious consequences)	Dose reduction by 50%, or temporary drug cessation until resolution to grade ≤ 2 or baseline ^a (at the discretion of investigator)	5 mg BID for at least 2 weeks before considering dose escalation ^b
Grade 2 or lower neutropenia or thrombocytopenia; and grade 3 or lower anemia (hemoglobin <8 g/dL)	Maintain dose or dose reduction by 50% (at the discretion of investigator)	If dose reduced, dose escalation at the discretion of the treating physician

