5.5.1 Baseline assessment (-28 days)

Assessments at the time of enrollment will include:

- History and physical exam including Karnofsky performance status
- Clinical laboratory parameters (hematology, serum chemistry, lipid levels, pancreatic enzymes, Hepatitis B and C), and pregnancy testing in women with reproductive potential.
- Electrocardiogram (EKG)
- Comprehensive GVHD assessment including digital pictures of range of motion (if abnormal) and any visible skin lesions, mapping of sclerotic areas (Appendix I)
- Patient reported outcomes
- Research blood collection for correlative studies

5.5.2 Safety Monitoring (Study Days 14 and 28, End of Month 2, 4, and 5)

Subjects will undergo hematology and serum chemistry testing in 2 and 4 weeks +/- 4 days, then monthly +/- 14 days while receiving ruxolitinib. Lipid levels will be checked at the end of 2 months +/- 14 days. Pancreatic enzymes should be checked if triglyceride level ≥ 500 mg/dl. These laboratories may be tested locally if more convenient for the subject. When tests are done locally, and not at the study center, the subject will receive a phone call from the study personnel if there are abnormal results. All observed grade 3 or above treatment-emergent adverse events (new or worsening from baseline) and all serious adverse events will be collected. CTCAE version 4.03 (Appendix H) will be utilized to grade the severity of adverse events. Please also see sections 5.5.6 and 7.0.

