8.1.10 Drug toxicities

The following drug toxicities were noted in trials mostly involving patients with myelofibrosis and polycythemia vera.

Blood and lymphatic system disorders:

Anemia (40.8-82.4%), thrombocytopenia (16.8-69.8%), neutropenia (16.6%). Also includes febrile neutropenia. Cytopenias are dose dependent and reversible with dose reduction/interruption.

Infections and infestations:

Urinary tract infections (6-12.6%) Including urosepsis, Cystitis, Kidney infection, Urinary tract infection bacterial, Nitrite urine present, and pyuria. Pneumonia (8.3%) Herpes zoster (4.0-4.3%) Tuberculosis (0.3%)

Gastrointestinal disorders:

Flatulence (3.3%) and Constipation (8.7%).

Hepatic dysfunction:

Raised alanine aminotransferase (22.3-27.2%) and aspartate aminotransferase (19.9-26.1%)

Metabolism and nutrition disorders:

Weight gain (7.6-12.3%), Hypercholesterolemia (16.9-20.7%), Hypertriglyceridemia (9.8%)

Nervous system disorders:

Dizziness (12.0-15.3%), Headache (14.0%)

Skin and subcutaneous tissue disorders:

Bruising (21.6%) including hematoma, petechiae and purpura

Vascular disorders:

Hypertension (6.5%)

General disorders and administration site conditions:

In clinical studies in myelofibrosis, fatigue, bone pain, pyrexia, pruritus, night sweats, splenomegaly and weight loss noted in 60.4% after discontinuation of ruxolitinib.

In a retrospective study of ruxolitinib in patients with chronic GVHD, cytopenia and CMV reactivation was observed in 17% and 15% of patients. Cytopenias preceded the use of ruxolitinib in most of the patients (15%).

Progressive Multifocal leukoencephalopathy (PML) has been reported with ruxolitinib treatment. Physicians should be alert for neuropsychiatric symptoms suggestive of PML. If PML is suspected, further dosing must be suspended until PML has been excluded.

Non-melanoma skin cancers (NMSCs), including basal cell, squamous cell, and Merkel cell carcinoma have been reported in patients treated with ruxolitinib. Most of these patients had histories of extended treatment with hydroxyurea and prior histories of NMSC or pre-malignant skin lesions. A causal relationship to ruxolitinib has not been established. Periodic skin examination is recommended for patients who are at increased risk for skin cancer.

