9.1 Definitions

Adverse Event

An adverse event (AE) is defined as any untoward medical occurrence in a clinical trial subject administered a pharmaceutical product and which does not necessarily have a causal relationship with this treatment. An adverse event can therefore be any unfavorable and unintended sign (including an abnormal laboratory finding, for example), symptom, or disease temporally associated with the use of a medicinal (investigational) product, whether or not the event is considered causally related to the use of the product.

An elective surgery or procedure that is scheduled to occur during a study will not be considered an adverse event if the surgery or procedure is being performed for a pre-existing condition and the surgery or procedure has been planned before study entry. However, if the pre-existing condition deteriorates unexpectedly during the study (*e.g.*, the surgery is performed earlier than planned), then the deterioration of the condition for which the elective surgery or procedure is being done will be considered an adverse event.

Any worsening of a pre-existing condition or illness is considered an adverse event. Laboratory abnormalities and changes in vital signs are considered to be adverse events if they result in discontinuation from the study, necessitate therapeutic medical intervention, require dose modifications and/or if the investigator considers them to be adverse events.

Unexpected Adverse Event

An unexpected adverse event is any adverse drug event that is not listed in the current labeling/Investigator's Brochure. "Unexpected," as used in this definition, refers to an adverse drug experience that has not been previously observed (*i.e.*, included in the labeling) rather than from the perspective of such experience not being anticipated from the pharmacological properties of the pharmaceutical product.

Serious Adverse Event

A serious adverse event is one that at any dose (including overdose) and regardless of causality:

- Results in death
- Is a serious threat to life, health, safety or welfare-fare of subject ¹
- Requires inpatient hospitalization or prolongation of existing hospitalization
- Requires intervention to prevent permanent impairment or damage
- Results in persistent or significant disability or incapacity²
- Is a congenital anomaly or birth defect
- Is another serious important medical event³

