10.2 Analysis plan

Descriptive statistics will be computed for subject characteristics. Mean, standard deviation (SD), median and range will be reported for continuous variables and frequencies and percentages will be used to describe categorical variables.

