10.2.3 Safety endpoint

Safety endpoints will be assessed on the safety analysis set. All adverse events recorded during the study will be summarized by each subject. The incidence of treatment-emergent adverse events (new or worsening from baseline) will be summarized by severity and type of adverse event. Listings of deaths, severe adverse events, and adverse events leading to early termination of study treatment or premature withdrawal from study will also be provided.

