Information regarding the actual treatments, adverse events, and laboratory tests are to be recorded on appropriate forms. See attached Data forms. Serious adverse events, when noted, will be recorded on site via the standard serious adverse effects form.

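### No analysis of the scheduled blood counts, chemistry and lipids is planned, so lower-grade and unacted-on laboratory changes may be under-counted in the safety tables

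*Combined protocol and SAP*

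**What the plan says.** **Analysis.** Section 10.2.3 works on the safety set and deals only with adverse events: "The incidence of treatment-emergent adverse events (new or worsening from baseline) will be summarized by severity and type of adverse event". Its listings are of the same kind: "Listings of deaths, severe adverse events, and adverse events leading to early termination of study treatment or premature withdrawal from study will also be provided". The general statement in Section 10.2 goes no further: "Descriptive statistics will be computed for subject characteristics". Section 10.4 adds summaries of grade 3 and above or serious events, and listings for the data and safety monitoring committee. No hematology, chemistry or lipid parameter is named in any of these places.

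**Measurement.** Section 5.5.2 states "Subjects will undergo hematology and serum chemistry testing in 2 and 4 weeks", and then monthly while on drug. The table in Section 7.0 adds a baseline sample for both, and lipids at baseline and month 2. Section 11.0 covers recording: "Information regarding the actual treatments, adverse events, and laboratory tests are to be recorded on appropriate forms".

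**Definition.** Section 9.1 sets out when a laboratory value is an event. It begins "Laboratory abnormalities and changes in vital signs are considered to be adverse events if they result in discontinuation from the study" and goes on to three further routes: therapeutic intervention, dose modification, or the investigator's own judgement.

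**Dose table.** Section 5.2 lets the dose be kept for "Grade 2 or lower neutropenia or thrombocytopenia; and grade 3 or lower anemia".

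**The concern.** The main known harms listed in Section 8.1.10 include laboratory findings: low counts, raised transaminases, and raised cholesterol and triglycerides. These are measured on a schedule. The plan nevertheless reports them only through a filter, namely whether someone acted on the value or chose to call it an event. In a multicenter trial that also permits local laboratory testing, this makes the reported rates partly a property of the sites.

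Baseline adds to this. Section 3.1 admits platelets from 50,000/µL and neutrophils just above 1000/µL, which are the upper edges of the grade 3 ranges in Section 5.2. Neither 3.1 nor 3.2 sets a hemoglobin minimum. In a single-arm trial, comparing each subject's worst value with his or her own baseline is the direct way to show worsening on treatment. Section 10.2.4 plans change from baseline for patient-reported outcomes and biomarkers, but there is no counterpart for the safety laboratories.

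**Working it through.** The plan states no figure on this point, so the check is mainly a comparison of sections, followed by one calculation for scale.

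**Step 1. Is any analysis of measured values planned?** Sections 10.2, 10.2.1, 10.2.3, 10.2.4 and 10.4 cover subject characteristics, efficacy endpoints, adverse events, patient-reported outcomes with correlative biomarkers, and mortality monitoring with adverse-event summaries. None covers safety laboratory values.

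**Step 2. How does a value reach the 10.2.3 tables?** It must first become an adverse event under 9.1, by action (discontinuation, treatment, dose change) or by judgement. The table in 5.2 shows where action is built in. That table applies only to toxicity at least possibly related to ruxolitinib.

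| Finding (drug-related) | Response in 5.2 | Automatic event under 9.1? |
|---|---|---|
| Grade 4 neutropenia or thrombocytopenia | Interruption, mandatory | Yes |
| Grade 3 neutropenia or thrombocytopenia | Reduction or interruption (investigator chooses) | Yes, both are dose changes |
| Grade 3-4 hepatic or renal | Interruption, mandatory | Yes |
| Grade 3 or lower anemia | Dose may be kept | No, unless treated or judged an event |
| Grade 3 or lower amylase or lipase | Dose may be kept | No, unless treated or judged an event |
| Grade 1-2 changes, including lipids | Dose may be kept | No, unless treated or judged an event |

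A value judged unrelated to drug falls outside the table, so no dose change is prescribed for it.

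**Step 3. Is there a grade threshold on collection?** Section 5.5.2 says that grade 3 or above treatment-emergent events and all serious events are collected. Section 9.2.2 says that events are collected from consent to 30 days after the last dose, with no grade limit. If 5.5.2 governs, non-serious grade 1-2 laboratory events never reach the tables, and the summary by severity in 10.2.3 is cut off at grade 3. If 9.2.2 governs, they can reach the tables, but only by action or judgement.

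**Step 4. Scale.** Inputs: 47 subjects dosed (Section 10.1); cytopenia in 17% of the retrospective chronic GVHD series (Section 8.1.10). It is an assumption that this rate carries over.

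- Expected subjects with cytopenia = 47 × 0.17 = 7.99, about 8.
- Exact (Clopper-Pearson) 95% interval for 8/47: 7.6% to 30.8%.
- Number recorded = 8 × share recorded. The share is not in the documents. At 25%, 50% and 75% the tables would show 2, 4 and 6 subjects; the full range is 0 to 8.

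Section 8.1.10 adds that cytopenia preceded ruxolitinib in most of these patients (15%). If that percentage has the same denominator, 47 × 0.15 = 7.05, so about 7 of the 8 would have been cytopenic before treatment. This shows why a baseline comparison is needed to interpret the count.

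**The case against.** The strongest reply is that the serious laboratory toxicity is already captured. Drug-related grade 3-4 neutropenia, thrombocytopenia, hepatic and renal toxicity prompt a dose change and so become events. Anemia that is transfused qualifies through treatment. Section 9.2.2 sends every grade 3 or higher event to the monitoring committee regardless of attribution. Treatment-emergent already means new or worse than baseline. All of this stands, and it confines the exposure to the remaining categories. The amylase and lipase row is also narrow, because after baseline these enzymes are required only when triglycerides reach 500 mg/dL.

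Three stronger readings are tempting, and the documents do not support them.

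- A reader might infer that a laboratory value counts only if acted on. Section 9.1 lets the investigator's judgement suffice, and its general definition of an adverse event includes abnormal laboratory findings.
- A reader might infer that under-reporting is certain. The recorded share could be anything from none to all.
- A reader might apply the other rates in Section 8.1.10 to 47 subjects (for anemia, 47 × 0.408 = 19.2 to 47 × 0.824 = 38.7) and take the result as cases missed. Those rates come mostly from myelofibrosis and polycythemia vera, and the products are expected totals, not omissions.

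It can also be said that safety is not a listed objective, that restricting collection to grade 3 and above may be a deliberate scope choice, and that tables can be added before analysis. The scope choice is possible, but then 9.2.2 and the by-severity summary should say so. That the tables can still be added is a reason to add them now.

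Finally, the data forms are in a Study Site Manual that is not part of these documents, so it cannot be confirmed that local values are entered with their reference ranges. That stands, and it is carried into the fix.

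**Conclusion.** The gap is real: the plan measures and records the laboratory values but analyses none of them. An abnormality reaches the tables only through action or investigator judgement, and possibly only at grade 3 or above. Grade 1-2 changes, anemia up to grade 3 left without treatment or dose change, lipid changes and values judged unrelated to drug may be under-counted. Drug-related grade 3-4 neutropenia, thrombocytopenia, hepatic and renal toxicity are not part of the problem, provided that the dose table is followed.

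The size of any under-count cannot be derived from the documents. About 8 of 47 subjects with cytopenia indicates scale only, and rests on the retrospective chronic GVHD rate applying here. The efficacy conclusion and the mortality boundary are unaffected. The point should be corrected because a better method than event records alone is available with little or no new data collection.

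**What to change.** In Section 10.2.3, on the safety set and derived from the recorded laboratory values:

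- Tabulate the worst on-treatment CTCAE 4.03 grade, and the shift from baseline to worst grade, for hemoglobin, platelets, neutrophils, ALT, AST, bilirubin and creatinine.
- Tabulate the shift from baseline to month 2 for cholesterol and triglycerides, the only scheduled on-treatment lipid sample.
- Report the proportion of subjects with a new grade 3 or higher value, with an exact 95% confidence interval, whether or not an adverse event was recorded.

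Confirm that values from local laboratories are entered, together with the reference ranges needed for grades defined by the upper limit of normal. Reconcile the collection statements in Sections 5.5.2 and 9.2.2, and align the by-severity summary in 10.2.3 with the outcome.

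Cost: a set of programmed tables, and some data entry if local values or ranges are not yet captured. No new tests, no change to the sample size and no change to clinical management. The laboratory toxicity rates may look less favourable than the adverse-event tables alone.

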10.2.4 Analysis of patient reported outcomes and Correlative data

Descriptive statistics will be computed for patient reported outcomes Lee Chronic GVHD Symptom Scale, and Scleroderma Health Assessment Questionnaire at study enrollment and 6 months. Changes in patient reported outcomes from study enrollment to 3 and 6 months will be assessed with paired t-tests or Wilcoxon sign rank test depending on whether test assumptions are met.

For **correlative studies**, changes in measured parameters from baseline to defined time points after therapy initiation will be measured. We will graphically display biomarker levels over time for each subject individually as well as averages at each time point for responders and non-responders separately. Univariate and multiple logistic regression will be used to determine if the change in biomarker level from baseline to 3 and 6 months is predictive of responder status at 6 months, looking at the biomarkers individually as well as in combination.

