5.1 Treatment Schedule and Administration: Ruxolitinib

Drug	Dose/Frequency	Duration	Administration
Ruxolitinib	10 mg BID	6 months, may extend up to 12 months	Oral

Subjects will receive oral ruxolitinib at a dose of 10 mg twice daily. Doses may not exceed 10 mg twice daily. Subjects will record their intake on a medication diary provided to them. Ruxolitinib will be continued for 6 months, unless there is intolerable toxicity, chronic GVHD progression requiring additional systemic treatment or relapse of the underlying malignancy. Subjects with mixed responses or chronic GVHD progression prior to 6 months of therapy that does not require initiation of additional agent are allowed to continue ruxolitinib for the complete 6 month duration. Therapy duration of 6 months will ensure adequate exposure to ruxolitinib, and is important because of the limited options for therapy in the study population and limitations of the current response assessment.

Extended treatment

Subjects who continue to have stable disease, mixed responses or partial/complete responses at the end of 6 months may continue the drug for a total of 12 months. Subjects with chronic GVHD progression (not including stable disease or mixed responses) at the end of 6 months will stop ruxolitinib, regardless of whether or not a new systemic therapy has been added.

Ruxolitinib taper prior to discontinuation

At the end of 6 months, or 12 months for subjects treated on extension study, ruxolitinib will be tapered over a month before discontinuation, for example, a dose reduction by 5 mg every 1-2 weeks. Ruxolitinib may be stopped without a taper in cases of unacceptable toxicities. If an UNMC IRB # 333-18, Protocol Version 1.6 dated 25Jan2021

abrupt cessation of ruxolitinib is required, investigators are strongly encouraged to consider starting or dose-escalating systemic glucocorticoid (prednisone dose ≥ 0.5 mg/kg/day or equivalent dose) for at least a week to avoid rebound symptoms. While coming off ruxolitinib, subjects should be carefully monitored for worsening of GVHD symptoms or any other withdrawal symptoms.

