5.4 Duration of Study and Follow-up

We estimate that there will be 47 subjects dosed over a 2.5-year period. After accrual is met, we plan to follow the subjects for up to 2 years; the follow-up duration is discussed in detail in the table below.

GVHD response evaluation every 3 months	Therapy duration	End of therapy safety evaluation (30-40 days after the last dose of the study drug)	Last follow-up for GVHD evaluation	Data collection
Stable disease or mixed responses at the end of 6 months	6 to 12 months followed by taper over 1 month ¹	8 months; If therapy continued till 12 months and tapered over the next month, 14 months ²	At the end of 6 months; If therapy continued until 12 months, up to 24 months from the study enrollment ³	Data on survival, relapse of malignancy, subsequent GVHD treatment will be collected till subjects are removed from the study, death or up to a total of 2 years. For subjects who have completed last follow-up for GVHD evaluation, further data may be collected via review of medical records or telephone interview.
Partial/complete responses at the end of 6 months	6 to 12 months followed by taper over 1 month ¹	8 months ⁴ ; If therapy continued till 12 months and tapered over the next month, 14 months ²	Up to 24 months from the study enrollment ³	
GVHD progression, toxicity or relapse ⁵	<6 months (may stop without a taper)	About 30 days after the last dose	At the end of 6 months	

¹If no intolerable toxicity, chronic GVHD requiring initiation of an additional systemic agent, or relapse of underlying malignancy within the 6 months of the study participation, ruxolitinib may be continued till 12 months

²If no toxicity concerns were raised at 12-month follow-up, this evaluation may be performed over the phone with a plan to see the subject in a follow-up at 15 months.

³The subject will be followed every 3 months until progression of chronic GVHD requiring initiation of an additional systemic agent, relapse of underlying malignancy or for a total of 2 years

⁴For subjects with partial or complete responses at 6 months, if no toxicity concerns were raised at 6-month follow-up, this evaluation may be performed over the phone with a plan to see the subject in a follow-up at 9 months.

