5.5.4 End of Month 6 Visit (+/-14 days)

Assessments at the end of month 6 visit will include:

- History and physical exam
- Clinical laboratory parameters (hematology and serum chemistry)
- Comprehensive GVHD assessment including digital pictures of range of motion (if abnormal) and any visible skin lesions, mapping of sclerotic areas (Appendix I)
- Patient reported outcomes
- Research blood collection for correlative studies
- Adverse event monitoring

Data on relapse of the underlying malignancy, survival, chronic GVHD flares, prednisone dose and use of other immunosuppressive agents will be captured at scheduled time points, and verified at each visit.

5.5.5 End of Month 9, 12, 15, 18, 21 and 24 Visit (+/-30 days) (Extended Treatment)

Subjects who maintain complete or partial response at the end of 6 months, OR receive extended therapy (see section 5.4 for details) will be followed every 3 months (+/-30 days) until start of another systemic treatment for chronic GVHD, relapse of underlying malignancy or for a total of 2 years to determine the duration of response.

Assessments at these visits will include:

- History and physical exam
- Clinical laboratory parameters (hematology and serum chemistry)
- Comprehensive GVHD assessment including digital pictures of range of motion (if abnormal) and any visible skin lesions, mapping of sclerotic areas (Appendix I)
- Patient reported outcomes
- Adverse event monitoring if receiving ruxolitinib within the past 30 days

Data on relapse of the underlying malignancy, survival, chronic GVHD flares, prednisone dose and use of other immunosuppressive agents will be captured at scheduled time points, and verified at each visit.

5.5.6 End-of-therapy or Safety Follow-up Visit (30-40 days after the last dose of ruxolitinib)

Subjects will undergo this visit 30-40 days after the last dose of ruxolitinib (see section 5.4 for details).

Assessments at safety follow-up visit will include:

- History and physical examinations
- Clinical laboratory parameters (hematology and serum chemistry)
- Comprehensive GVHD assessment (if a subject withdraws from study treatment prior to 3 or 6 month assessment time points)
- Adverse event monitoring

Subjects with grade 3-4 toxicities are required to undergo close monitoring with repeat testing of any abnormal laboratory or clinical parameter(s) within 2-7 days depending on specific circumstances.

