5.6 Criteria for Discontinuation of the Study Drug and Removal from Study

Subjects will discontinue the study drug for any of the following reasons:

- Progression of GVHD resulting in initiation of a new systemic immunosuppressive agent (also see Section 5.1.1)
- Development of an adverse reaction that necessitates discontinuation of the study drug, including any unresolved serious adverse event. Please see section 5.2 for further details.
- Development of a serious systemic allergic response or severe degree of intolerance to the study medication.
- Development of intercurrent medical problems that would make continued protocol therapy detrimental to the subject's safety.
- The subject chooses to discontinue treatment.

Subjects who stop study medication for GVHD progression or relapse of underlying malignancy will stop research visits except for the safety follow-up visit. Data may continue to be collected via chart review.

Subjects will be removed from the study (**study withdrawal**) for any of the following reasons:

- If at any time the requirements of this protocol are detrimental to the subject's wellbeing, the subject will be removed from the study. In this event, the reason(s) for withdrawal will be documented.
- The subject requests removal from the study.

The reason(s) for **study withdrawal** will be documented and no further information may be collected on the subject. The reason(s) for stopping study medication will be documented in the UNMC IRB # 333-18, Protocol Version 1.6 dated 25Jan2021

case report form. If available, the following information will be recorded in the case report form: GVHD status, date of relapse of underlying malignancy, date of death, cause of death, and autopsy report. Subjects who stop the study drug but do not withdraw from the study may remain in the study.

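### The paired tests of patient-reported change use only subjects with both scores, and month-6 questionnaires are likely to be missing more often in those doing worse

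*Combined protocol and SAP*

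**What the plan says.** Change in patient-reported outcomes between enrollment and 6 months is exploratory objective 3 (Section 1.3). Section 10.2.4 gives the analysis: changes from enrollment to months 3 and 6 "will be assessed with paired t-tests or Wilcoxon sign rank test depending on whether test assumptions are met". It names no analysis set, no handling of missing questionnaires or deaths, and no sensitivity analysis. The full analysis set in Section 10.1 keeps early treatment failures and deaths, but Section 10.2.1 applies that set only to the primary analysis.

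These sections decide who has a month-6 questionnaire:

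- Section 5.1.1 treats a new systemic agent for chronic GVHD as therapy failure, and ruxolitinib is then discontinued.
- Section 5.6: "Subjects who stop study medication for GVHD progression or relapse of underlying malignancy will stop research visits except for the safety follow-up visit". It adds: "Subjects who stop the study drug but do not withdraw from the study may remain in the study".
- Section 5.5.6 lists the content of the safety visit. It includes "Comprehensive GVHD assessment (if a subject withdraws from study treatment prior to 3 or 6 month assessment time points"), but no questionnaire. The Section 7.0 schedule agrees: patient-reported outcomes are marked at baseline, months 3 and 6 and the later three-monthly visits, and not at the safety visit.
- Section 5.1: "Subjects with mixed responses or chronic GVHD progression prior to 6 months of therapy that does not require initiation of additional agent are allowed" to stay on ruxolitinib for the full 6 months.
- The Section 5.4 table has a row "GVHD progression, toxicity or relapse" for subjects who stop before 6 months. It puts their last GVHD evaluation at the end of 6 months.

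**The concern.** The plan treats the two kinds of outcome differently in the same subjects. For response, an early failure stays in the denominator as a non-responder, and the safety visit recovers a clinician GVHD assessment. For the questionnaires, the same subject has no month-6 score and drops out of the paired comparison without mention. A month-3 score, if there is one, feeds only the separate month-3 test.

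The reason for the missing score (progression that needs a new agent, relapse, death) is tied to a poor course. Section 2.0 says that sclerotic GVHD is hard to assess and that patient-reported measures can give valuable insight. With a single open-label arm, no control group shares the attrition. A completer mean could be read as benefit when part of it reflects who was left to measure.

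**Working it through.** **There is no plan figure to reproduce.** The documents state no SD, effect size, power or missing share for these outcomes. The nearest figure is the dropout allowance in Section 10.1: 42 / (1 − 0.10) = 46.7, rounded up to 47. Treatment failures remain among the evaluable subjects for the primary endpoint, so failures without a month-6 questionnaire would come on top of unrelated dropout.

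**Step 1: who contributes a month-6 pair.**

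| Course before month 6 | Month-6 questionnaire under the plan |
|---|---|
| On drug, including progression that needs no new agent | Yes (5.1, 5.5.4) |
| Stops drug for progression or relapse | Visits end, safety visit only (5.6). The 5.4 table implies a 6-month GVHD evaluation but does not mention questionnaires |
| Stops drug for toxicity or by choice | Not named in the 5.6 visit stop; may remain in the study |
| Death or study withdrawal | None |

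The second row and the deaths are the outcome-related losses.

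**Step 2: general size.** Let f be the missing share, C the mean change in completers and M the mean change that the missing subjects would have shown, with improvement positive. The overall mean is (1 − f)C + fM, so

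bias of the completer mean = C − [(1 − f)C + fM] = f × (C − M).

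Assumptions: 47 subjects, no true overall change, SD of change 1, two-sided 5% test. The chance of a false significant improvement is nominally 2.5%.

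| f | Gap C − M | Bias | False improvement |
|---|---|---|---|
| any from 10% to 40% | 0 | 0 | 2.5% |
| 10% | 0.25 SD | 0.025 SD | 3.8% |
| 20% | 0.5 SD | 0.10 SD | 8.8% |
| 30% | 0.5 SD | 0.15 SD | 13% |
| 30% | 1.0 SD | 0.30 SD | 39% |
| 40% | 1.0 SD | 0.40 SD | 53% |

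A bias as large as the SHAQ threshold of 0.2 in Section 2.0 would need, at f = 30%, a gap of 0.2 / 0.30 = 0.67 SHAQ points.

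**Step 3: a specific mechanism.** Assumptions: 42 subjects, no true change, month-3 and month-6 changes bivariate normal with correlation 0.6, and the log-odds of a missing month-6 score falling by the stated slope per SD of month-3 improvement. Rejection is two-sided at nominal 5%.

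| Missing | Slope | Completer bias | Rejection |
|---|---|---|---|
| 10% or 25% | 0 | 0 | 5% |
| 10% | 1.0 | 0.05 SD | 6% |
| 10% | 1.5 | 0.07 SD | 8% |
| 25% | 1.0 | 0.13 SD | 11% |
| 25% | 1.5 | 0.16 SD | 15% |

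An estimate that also uses the month-3 score has bias below 0.01 SD in every row.

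**Step 4: how far that remedy reaches.** Step 3 makes missingness depend only on an observed score, which is the condition under which a likelihood method is unbiased. With 25% missing and slope 1:

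- If half of the missing subjects have no month-3 score either, the remaining bias is 0.06 SD.
- If none of them has one, it is 0.13 SD, the same as for completers.
- If missingness depends on the month-6 change itself, it is 0.14 SD, against 0.21 SD for completers.

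**The case against.** Four points deserve weight.

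1. A reader might infer that visits stop at any progression. They do not. Progression that needs no new agent can stay on drug to month 6 with questionnaires collected, and the visit stop in 5.6 does not name toxicity or subject choice. The 5.4 table even points to a 6-month GVHD evaluation after early stopping, in conflict with 5.6. This narrows the group affected but does not remove it.

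2. A reader might infer that the estimate is known to be biased toward improvement. The documents do not show that. Relapse of malignancy need not worsen skin or function scores. Subjects given a new systemic agent might score better at month 6 if measured, so the direction depends on the estimand, which is not stated. This stands, and "likely" is as far as the claim can go.

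3. A reader might infer that a mixed model cures the problem. Step 4 shows that it does so only for subjects with a post-baseline score whose missingness is explained by observed values. This also stands.

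4. The endpoint is exploratory, has no stated alpha or power, and drives no decision. Section 2.0 says that these measures add to objective change and do not replace it. Early failures are visible in the primary analysis and in the Kaplan-Meier estimate of treatment failure. All of this limits the consequence. It is not a reason to leave the questionnaire analysis without a population or a missing-data rule when the remedy is cheap.

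**Conclusion.** The concern holds in a limited form. As written, the plan gives a completer estimate, and the month-6 losses it creates are linked to treatment failure. Optimism is the expected direction but is not certain. On the assumptions of Step 3 with slopes of 1 to 1.5, the bias is about 0.05 to 0.07 SD at 10% missing and 0.13 to 0.16 SD at 25% missing, with 6% to 8% and 11% to 15% rejection at nominal 5%. It is zero when missingness is unrelated to outcome. The missing share, correlation and slope are all assumptions, because the documents supply none of them. The primary endpoint and its conclusion are unaffected.

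**What to change.** In Section 10.2.4:

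- Make the main estimate a mixed model for repeated measures on baseline, month 3 and month 6, including all subjects with a post-baseline score. The paired tests can stay as a secondary description.
- Add the proportion of all dosed subjects whose SHAQ falls by at least 0.2, counting treatment failure or death before month 6 as not improved. State how scores missing for other reasons are counted.
- Report the number of missing scores and the reasons at each visit.

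Reconcile Sections 5.4 and 5.6 on whether subjects who stop early for progression or relapse have a 6-month evaluation, and state whether questionnaires belong to it.

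The cost is a paragraph of analysis text and a standard model on data already collected. The downside is that the mixed model assumes missing at random and does not recover subjects with no post-baseline score. For them only the responder proportion helps.
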